### 7.2. EVALUATIONS BY VISIT

### 7.2.1. Study Day 1 (Dosing initiation)

Subjects who complete PTI-125-04 will be eligible to consent to this open-label extension. The Study Day 1 visit will occur in conjunction with the Month 24 visit of PTI-125-04.

Subjects will come to the clinic and, in addition to the Month 24 Visit activities for PTI-125-04, the following will be conducted:

Informed Consent

The following end of study procedures required at the Month 24 Visit for the completion of study PTI-125-04 will serve as baseline information for this open-label extension study:

- Review of concomitant medications
- Full physical examination including measurement of vital signs (blood pressure, temperature, pulse, and respiratory rate), height, weight
- C-SSRS Since Last Visit version. If the C-SSRS indicates imminent risk for suicidality, defined as the subject positively endorsing questions 4 or 5 of the suicidal ideation section or any suicidal behavior questions, discontinue study drug and refer for appropriate care.
- Blood and urine sample collection for clinical laboratory tests
- ECG
- Adverse event monitoring

Subjects will be administered one (1) tablet of study drug at the clinic. Subjects will be discharged with their supply of study drug until the next visit. They will be instructed

to take study drug twice daily, with or without food. A dose can be up to 4 hours late, but if a dose is missed, the next dose should NOT be doubled.

For all follow-up visits, subjects will be instructed to bring their study drug bottle to the clinic and a new bottle of study drug will be dispensed.

All follow-up visits can be  $\pm 10$  (ten) days for flexibility.

### 7.2.2. Follow-up Visits on Weeks 12, 36, 60, and 84

Subjects will return to clinic and the following assessments will be conducted:

- Height
- Weight
- Brief physical exam
- Measure vital signs (blood pressure, temperature, pulse, and respiratory rate)
- Adverse event monitoring
- Use of concomitant medications
- C-SSRS Since Last Visit version. If the C-SSRS indicates imminent risk for suicidality, defined as the subject positively endorsing questions 4 or 5 of the suicidal ideation section or any suicidal behavior questions, discontinue study drug and refer for appropriate care.
- Receive and count remaining tablets in each returned bottle of investigational product to assess adherence to BID dosing.

### 7.2.3. Follow-up Visits on Weeks 24 and 72

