### 9. ADVERSE EVENTS/SERIOUS ADVERSE EVENTS

### 9.1. ADVERSE EVENTS - DEFINITION

An adverse event (AE) is any undesirable event that occurs to a subject during a study, whether or not that event is considered study drug-related. Monitoring for AEs will start at dosing. Examples include:

- Any treatment-emergent signs and symptoms (events that are marked by a change from the subject's baseline/entry status [e.g., an increase in severity or frequency of pre-existing abnormality or disorder])
- All reactions from study drug, an overdose, abuse of drug, withdrawal phenomena, sensitivity, or toxicity to study drug
- Apparently unrelated illnesses
- Injury or accidents (Note: if a medical condition is known to have caused the injury or accident, the medical condition and the accident should be reported as two separate medical events [e.g., for a fall secondary to dizziness, both "dizziness" and "fall" should be recorded separately])
- Extensions or exacerbations of symptoms, subjective subject-reported events, new clinically significant abnormalities in clinical laboratory, physiological testing, or physical examination

All AEs, whether or not related to the study drug, must be fully and completely documented on the AE page of the eCRF and in the subject's clinical chart.

In the event that a subject is withdrawn from the study because of an AE, it must be recorded on the eCRF as such. The subject should be followed and treated by the Investigator until the abnormal parameter or symptom has resolved or stabilized.

The Investigator must report all directly observed AEs and all spontaneously reported AEs. The Investigator will ask the subject a non-specific question (e.g., "Have you noticed anything different since your dose of the study medication?") to assess whether any AEs have been experienced since the last assessment. AEs will be identified and documented on the eCRF in appropriate medical terminology. The severity and the relationship to the study drug will be determined and reported on the eCRF (see below).

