**eClinical Suite** 

## Table 1 - Schedule of Events for Active Participants.

STUDY PROCEDURE	Study Day 1	Week 12	Week 24	Week 36	Week 48	Week 60	Week 72	Week 84	Week 96	Repeat Visit A e	Repeat Visit B f	End of Study / Early Term
Informed Consent	X											
Vital Signs	X b	X	X	X	X	X	X	X	X	X	X	X
Height & Weight	X b	X	X	X	X	X	X	X	X	X	X	X
Physical Examination	Xbe	*	*	*	Χ°	*	*	*	Χ°	*	Хс	X °
Chemistry, Hematology, Urinalysis	X b		X		X		X		X		X	X
ECG	X b		X		X		X		X		X	X
Drug Dispensation d	X	X	X	X	X	X	X	X	X	X	X	
Drug Accountability		X	X	X	X	X	X	X	X	X	X	X
Adverse Events	X b	X	X	X	X	X	X	X	X	X	X	X
Concomitant Medications	X b	X	X	X	X	X	X	X	X	X	X	X
C-SSRS – Since Last Visit	X b	X	X	X	X	X	X	X	X	X	X	X

\* Brief physical exam.

<sup>e Repeat Visit A occurs 12 weeks following the Week 96 visit and then reoccurs every 24 weeks thereafter. f Repeat Visit B occurs 12 weeks following the first Repeat Visit A and then reoccurs every 24 weeks thereafter.

<sup>a Study Day 1 will take place during the Month 24 Visit for study PTI-125-04.

<sup>b Data collected at Month 24 Visit for study PTI-125-04 will be used.

<sup>c Full physical examination at Day 1 (as part of Month 24 Visit from study PTI-125-04), Week 48, Week 96, and Repeat Visit B, and at End of Study or Early Term Visit.

<sup>d Drug will be dispensed at Study Day 1 and every 12 weeks.

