## 6.3.2. Missing Data

### Partial or Missing Dates:

Missing data will not be imputed for the purpose of primary inference. All data recorded on the electronic case report form (eCRF) will be included in the safety data listings.

If complete Adverse Event (AE) start date is missing and AE end date is on or after the date of first dose, then the AE will be counted as a treatment emergent AE (TEAE) for the study.

If an AE has a partial missing start or stop date, the following rules will be used for imputation:

- If year is present but month and day are missing, impute start date as first dose date if the year is the same as the year of first dose date, otherwise January 1 of that year and impute stop date as last dose date if the year is the same, otherwise December 31 of that year.
- If year and day are present but month is missing, impute start month as first dose date
  month if AE start day greater than or equal to first dose day and if the year is the same,
  otherwise January and impute stop month as last dose date month if AE end day less than
  or equal to last dose day and if the year is the same, otherwise December of that year.
- If year and month are present but day is missing, impute start date as first dose day if the
  year and month are the same as the year and month of first dose date, otherwise first day
  of that month and impute stop date as last dose day if year and month are the same,
  otherwise last day of that month.

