### 8.1. Adverse Events

The Medical Dictionary for Regulatory Activities (MedDRA) dictionary (v27.0) will be used for coding AEs on the OLE Adverse Event eCRF.

Analyses of AEs will be performed for those events that are considered treatment emergent (TEAE), where treatment emergent is defined as any AE with onset or worsening on or after the First Study Dose in the OLE study and will be summarized for overall safety population.

The following summary tables will be presented:

- Overall Summary of TEAEs
- TEAEs by system organ class (SOC) and preferred term (PT)
- TEAEs by PT
- TEAEs by SOC, PT, and Maximum Severity
- TEAEs by SOC, PT, and Relationship to Study Drug
- Treatment Emergent Serious AEs (TESAEs) by SOC and PT

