## 8.2. Clinical Laboratory Evaluations

Listings of individual laboratory parameters by visit will not be presented. Significant laboratory results, as assessed by the Investigators, will be tabulated as AEs or SAEs and will appear in individual AE listings.

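### The SAP's partial-start-date rules check neither stop date nor prior recording, so adverse events known to precede the first OLE tablet can be counted as OLE treatment-emergent

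*SAP*

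**What the plan says.** Subjects coming from PTI-125-04 start the extension at that study's last visit. Protocol 7.2.1: "The Study Day 1 visit will occur in conjunction with the Month 24 visit of PTI-125-04". The procedures of that visit, including AE monitoring, laboratory samples and ECG, "will serve as baseline information for this open-label extension study". One tablet is then given in the clinic, so the first-dose date is the Month 24 date. In SAP Table 1 and Protocol Appendix B the Adverse Events cell for Study Day 1 carries footnote b: "Data collected at Month 24 Visit for study PTI-125-04 will be used".

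SAP 8.1 defines a TEAE as "any AE with onset or worsening on or after the First Study Dose in the OLE study". SAP 6.3.2 handles partial start dates as follows:

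- **Day missing:** "If year and month are present but day is missing, impute start date as first dose day" if month and year agree with first dose; otherwise the first of the month.
- **Month and day missing:** first-dose date if the year agrees; otherwise 1 January.
- **Month missing:** first-dose month if the year agrees and the known day is not before the first-dose day; otherwise January.

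Only a wholly missing start date is judged by the end date. SAP 6.3.2.1 then says that analyses use observed cases with no imputation.

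On findings from procedures, SAP 8.2 says "Significant laboratory results, as assessed by the Investigators, will be tabulated as AEs or SAEs". SAP 8.3 to 8.5 do the same for vital signs, examinations and ECGs, and none of these results is listed.

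**The concern.** Setting an unknown onset to the first dose is a sensible convention when the order of onset and dosing is unknown. Here the order may be on record: an event noted at Month 24 before the tablet, or one that had already stopped, began before OLE treatment. The rules do not use that information.

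The TEAE tables and listings are almost the whole safety output of this abbreviated SAP and may feed the DSUR. The study has one arm, so no comparator would expose misplaced events. Because laboratory and ECG results are not listed, a reader of the tables could not recognise a Day 1 abnormality as a baseline finding.

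**Working it through.** The plan gives no figure on this point, so there is none to reproduce. The check applies the SAP 6.3.2 rules and then the date test of SAP 8.1 (imputed start on or after first dose). All dates and time windows are assumptions; the documents give no AE dates and no rate of partial dates.

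**1. What each rule does.** First dose 15 June 2023:

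| Recorded onset | Imputed start | TEAE? |
|---|---|---|
| June 2023, day unknown | 15 June 2023 | yes |
| May 2023, day unknown | 1 May 2023 | no |
| 2023 only | 15 June 2023 | yes |
| 2022 only | 1 January 2022 | no |
| day 20, month unknown, 2023 | 20 June 2023 | yes |
| day 5, month unknown, 2023 | 5 January 2023 | no |

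Only onsets whose known parts fit the first dose are moved.

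**2. The contradictory record.** Take onset in June with the day unknown and stop on 3 June. The record places onset between 1 and 3 June. The rule gives 15 June, which is 15 − 3 = 12 days after the stop, and the event is a TEAE. If the start were wholly missing, the end date of 3 June would fail the SAP's test and the event would not be counted. Knowing the month makes the classification worse.

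**3. Share of truly pre-dose onsets converted.** Let onset fall evenly over the W days before dose, with each first-dose date in a 365-day year equally likely.

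- *Day missing.* Conversion needs onset in the first-dose month. A first dose on day d leaves d − 1 such days. The average is (7×465 + 4×435 + 378)/365 = 5,373/365 = 14.72 days. W = 30: 14.72/30 = 49%. W = 90: 16%. W = 180: 8%.
- *Month and day missing.* Conversion needs onset in the same calendar year. W = 30: (435 + 335×30)/(365×30) = 10,485/10,950 = 96%. W = 90: (4,005 + 275×90)/32,850 = 88%. W = 180: (16,110 + 185×180)/65,700 = 75%.
- *Month missing.* Enumerating every date gives 44.3%, 41.4% and 35.5% for the three windows, with impossible dates counted as not TEAEs. For first dose 15 June and W = 90, 48 of the 90 days have a day number of 15 or more. Two of these are a 31st and would give a 31 June, leaving 46/90 = 51%. This rule also errs the other way: of onsets within 90 days after dose, only 58.8% stay TEAEs.

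These shares are conditional on a partial date, a pre-dose onset and entry on the OLE form. They are not rates of error in the TEAE tables.

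**4. Day 1 findings, no imputation involved.** A significant result from a sample or ECG taken before the tablet, entered as an AE dated that day, has onset equal to the first-dose date. SAP 8.1 includes equality, and the SAP has no time-of-day or baseline exclusion, so it counts as a TEAE.

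**5. Do such events reach the analysis?** Footnote b and Protocol 7.2.1 bring Month 24 AE data into the extension. Protocol 9.1 points the other way: "Monitoring for AEs will start at dosing". SAP 8.1 says its dictionary "will be used for coding AEs on the OLE Adverse Event eCRF". No text says whether Month 24 events are entered on that form. The SAP does appear to allow for pre-dose events in the data: SAP 8.1 restricts its analyses to treatment-emergent events, and the date rules include outcomes that fall before first dose.

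**The case against.** The strongest reply is that the route is unproven. Footnote b also covers vital signs, weight and concomitant medications, and can be read as saying only that the parent-visit data are not collected twice. With Protocol 9.1 starting AE monitoring at dosing, Month 24 events may never be on the OLE form. This stands, and it makes the point conditional. It does not remove the gap, because the two texts pull apart and the SAP does not choose.

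Second, the AE examples in Protocol 9.1 refer to change from entry status and to new abnormalities, so a Day 1 value, being the baseline, is arguably not an AE. That helps, but these are examples, and a finding at Month 24 may be new relative to earlier PTI-125-04 visits.

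Third, SAP 6.3.2.1 may switch the date rules off. Read literally it would, but the same subsection goes on to fill in missing relationship and severity, so its scope is unclear and needs a sentence.

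Fourth, counting doubtful events as treatment-emergent is conservative and matches the SAP's treatment of missing relationship and severity. This is right when the order is unknown, but not when the record shows it.

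Fifth, Protocol 7.2.1 does not explicitly order AE monitoring before the tablet, so an event reported on Day 1 may be a reaction to that tablet. This stands, and the fix has to protect such events.

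**Conclusion.** The point holds as a conditional defect in a stated rule. If Month 24 events are on the OLE AE form and SAP 6.3.2 governs the tables, partly dated events whose known year, or year and month, match first dose can be classed as TEAEs although the record shows pre-dose onset. An imputed start can also fall after the recorded stop. The Day 1 sample or ECG route needs no imputation, only that the procedure preceded the tablet and the finding was entered as an AE with that date.

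A reader might infer three stronger things that the documents do not support:

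- **All partly dated Month 24 events become TEAEs.** Day-missing events from an earlier month and year-only events from an earlier year stay pre-dose, and the month-missing rule can send an event back to January.
- **The visit schedule shows what share of laboratory or ECG TEAEs are baseline findings.** Counting scheduled occasions gives a share of visits, not of events.
- **Events will be counted twice in the DSUR.** No text says how the two studies will be combined.

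The number of affected events cannot be determined from the documents. The correction is worth making before database lock because it changes how individual events are classified and costs little.

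**What to change.** Four changes to the SAP:

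1. In 6.3.2 add: *A partial start date is imputed to first dose only if the stop date is not before first dose and the record does not show onset before the first OLE tablet; otherwise the AE is classed as pre-dose.*
2. In 8.1 add: *AEs documented as starting before the first OLE tablet, including abnormalities found in pre-dose Study Day 1 procedures, are baseline events and are TEAEs only if they worsen after dosing. AEs starting after the tablet on Day 1, or of unknown order on Day 1, remain TEAEs.*
3. In 6.3.2.1 state that the no-imputation sentence does not override the AE date rules.
4. State whether Month 24 AEs are entered in the OLE AE dataset.

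The cost is a few sentences and one added condition in the TEAE flag. The second half of item 2 keeps in-clinic reactions to the first tablet in the tables. The downside is that a few events now counted conservatively would leave the TEAE tables.

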## 6.3.2.1. Imputation Methods

Observed cases, without imputation, will be used for the analyses.

If the relationship of an AE is missing, it will be considered treatment-related. Missing AE severity will be coded as severe.

## **Statistical Analysis Plan**

## 6.3.3. Handling of Early Termination Visit Information

If a participant is terminated early from this study the early termination visit data will be analyzed at the closest scheduled visit. If the closest visit has valid data, the early termination data will be assigned to the next available visit.

## 6.3.4. Coding Conventions for Events and Medications

All adverse events will be mapped to the Medical Dictionary for Regulatory Activities (MedDRA Version 27.0) system for reporting (preferred term and body system). Medical history will not be coded.

Prior and concomitant medications will not be coded.

## 6.3.5. Analysis Software

Data processing, tabulation of descriptive statistics, calculation of inferential statistics, and graphical representations will be performed primarily using SAS (release 9.4 or higher) for Windows. If the use of other software is warranted, the final clinical study report will detail what software was used and for what purposes.

## 6.3.6. Study Data

Study data identified in the schedule for time and events (Table 1) are collected, and source verified, on the electronic data capture tool: Axiom Fusion eClinical Suite (Axiom, Toronto, ON, Canada).

All study data will be formulated into regulatory compliant data sets to provide transparency, traceability, and integrity of trial analysis results from the collection source. Observed study data will be mapped to the CDISC Study Data Tabulation Model (SDTM) and serve as the source data from the trial. All study analyses will be completed using analysis data sets that are derived from the SDTM and follow the CDISC Analysis Data Model (ADaM) architecture. All planned analyses will be performed using the ADaM data sets developed for this study.

The following Implementation Guides will be referenced for the configuration of SDTM and

#### ADaM datasets:

- SDTM Model 1.7 and SDTM Implementation Guide (SDTM IG) version 3.3 will be used.
- ADaM Model 2.1 and ADaM Implementation Guide (ADaM IG) version 1.3 will be used.

## **Statistical Analysis Plan**

## 6.4. Planned Study Analyses

## 6.4.1. Statistical Summaries: Descriptive and Inferential

The classical summary of count and percentages will be provided for basic safety tabulation and dispositions as appropriate. All data will be presented in by-subject data listings.

No inferential statistics will be produced.

## 6.4.2. Interim Analyses

No formal interim analyses will be conducted.

## 7. SUMMARY OF STUDY DATA

## 7.1. Subject Disposition

A summary of the analysis sets includes the number and percentage for the following categories

- the number of subjects dosed in the original parent study (PTI-125-04 Safety Population)
- the number enrolled in the OLE (OLE Safety Population)
- the number of subjects who completed 96 weeks in the OLE (OLE Safety Population)
  - subject who completed 96 weeks in the OLE and reconsented and resumed study participation (OLE Safety Population) will be identified via footnote
- the number of subjects who discontinued treatment early in the OLE and reason(s) for discontinuation of treatment as recorded on the OLE eCRF

A by-subject data listing of study completion information including the reason for premature study withdrawal, if applicable, will be presented.

## 7.2. Protocol Deviations

Protocol deviations will not be presented in a data listing, as all subjects who received one dose of study drug during the OLE study will be included in the Subject Disposition and AE tabulations and individual Disposition and AE listings.

## **Statistical Analysis Plan**

## 7.3. Demographics and Baseline Characteristics

Individual participant demographics and baseline characteristics will be summarized and presented in data listings.

## 7.4. Medical and Surgical History

Re-entry of subjects based on current medical / surgical history was assessed by Investigator. These will not be presented in data listings, but are available in the source documents at the sites.

### 7.5. Prior and Concomitant Medications

Medication data will not be presented in data listings.

Study medication compliance will not be calculated. All subjects who took at least one dose of study drug will be included in the Subject Disposition and AE tabulations and individual Disposition and AE listings.

## 7.6. Concomitant Procedures/Non-drug Therapies

Concomitant Procedures/Non-Drug Therapies data will not be presented in data listings.

## 8. SAFETY ANALYSES

All safety analyses will be conducted using the Safety population.

### 8.1. Adverse Events

The Medical Dictionary for Regulatory Activities (MedDRA) dictionary (v27.0) will be used for coding AEs on the OLE Adverse Event eCRF.

Analyses of AEs will be performed for those events that are considered treatment emergent (TEAE), where treatment emergent is defined as any AE with onset or worsening on or after the First Study Dose in the OLE study and will be summarized for overall safety population.

The following summary tables will be presented:

- Overall Summary of TEAEs
- TEAEs by system organ class (SOC) and preferred term (PT)
- TEAEs by PT
- TEAEs by SOC, PT, and Maximum Severity
- TEAEs by SOC, PT, and Relationship to Study Drug
- Treatment Emergent Serious AEs (TESAEs) by SOC and PT

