### 7.2.8. Re-entry Day 1(Re-entry for Subjects Who Previously Completed)

Subjects who completed the final visit on the PTI-125-09 study on Amendment 1 or Amendment 2 will be eligible to re-enter this open-label extension study if the subject does not meet exclusion criterion.

Subjects will come to the clinic for a Re-entry Day 1 visit and the following will be conducted:

- Informed Consent
- Medical History- focused on any new conditions that occurred during the gap period between study completion and study re-entry
- Vital signs (blood pressure, temperature, pulse, and respiratory rate)
- Height
- Weight
- Full physical exam
- Adverse event monitoring
- Use of concomitant medications
- Clinical laboratory tests (blood and urine)
- ECG
- C-SSRS Since Last Visit version. If the C-SSRS indicates imminent risk for suicidality, defined as the subject positively endorsing questions 4 or 5 of the suicidal ideation section or any suicidal behavior questions, discontinue study drug and refer for appropriate care.
- Review of Inclusion and Exclusion criteria following all Re-entry Day 1

assessments and prior to dosing.

Subjects will be administered one (1) tablet of study drug at the clinic. Subjects will be discharged with their supply of study drug until the next visit. They will be instructed to take study drug twice daily, with or without food. A dose can be up to 4 hours late, but if a dose is missed, the next dose should NOT be doubled.

Follow-up visits will continue as indicated in Appendix C- Schedule of Events for Reentry Participants. For all follow-up visits, subjects will be instructed to bring their study drug bottle to the clinic and a new bottle of study drug will be dispensed (except at the Re-entry Week 4 visit if required).

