### 9.5. SERIOUS ADVERSE EVENTS REPORTING

The reporting of SAEs by the Sponsor to Regulatory Authorities (e.g., FDA) is a regulatory requirement.

All SAEs must be reported immediately (within 24 hours of learning of the event) via entry into the EDC system with at least the event term, start date, and IP relationship. In the event EDC entry is unavailable, notification must occur via email or phone to the contact below:

[name] Cassava Sciences, Inc.

Email: [contact]

[contact]

Do not delay reporting a suspected SAE to obtain additional information. Any additional information, if collected, can be reported to the Sponsor as a follow-up to the initial report.

If a partial SAE report was initially provided then a completed SAE report must be entered into the EDC within five (5) working days. The Investigator is responsible for reporting SAEs to the IRB according to IRB guidelines. The Sponsor will report SAEs to FDA as required.

In the case of a death or other SAE that has occurred within 30 days after receiving study drug, the Principal Investigator must also report such an event within 24 hours of being notified.

In the event of any SAE (other than death), the subject will be instructed to contact the study physician (Principal Investigator or designee) using the phone number provided in the ICF. All subjects experiencing an SAE will be seen by a Principal Investigator or designee as soon as feasible following the report of an SAE.

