## **Statistical Analysis Plan**

### 4. STUDY METHODS

## 4.1. General Study Design and Plan

This is a 96 week extension study of open-label simufilam 100 mg b.i.d. for subjects who completed the Phase 2 study, PTI-125-04 or who already completed participation in the PTI-125-09 study through Week 96 visit and reconsented to resume participation in the study through FDA approval of simufilam or program termination (Figure 1). All subjects will provide consent to enroll into this study. Simufilam will be administered as coated oral tablets.

The last study visit, Month 24, from the PTI-125-04 study will be used for the Study Day 1 visit assessments in this extension study. Clinic visits will occur every 12 weeks ±10 days as outlined in Table 1– Schedule of Events for Active Participants.

Subjects who already completed participation through Week 96 in PTI-125-09 will have the option to return to the study and resume participation. After the subject provides consent, the Investigator will confirm that the subject continues to satisfy both the inclusion and exclusion criteria. The study drug will be administered at the research site on Re-entry Day 1 and subsequent visits will be scheduled. The length of their participation gap will dictate which visits apply to them according to Table 2 – Schedule of Events for Reentry Participants.

For active subjects, a full physical examination (general appearance, chest/lungs, heart, abdomen, skin, musculoskeletal, Neurologic, Vascular, and Immunologic) will be performed at Study Day 1, Week 48, and Week 96, and Repeat Visit B until study end. For re-entry subjects, a full physical examination will occur on Re-entry Day 1 and Repeat Visit B thereafter until study ends. All subjects will return to the clinic every 12 weeks for AE monitoring, vital sign measurements, height, weight, Columbia Suicide Severity Rating Scale (C-SSRS) Since Last Visit version, and drug dispensation and accountability. Some re-entry participants will require a Re-entry week 4 visit. A brief physical exam (general appearance, cardiovascular, pulmonary, and abdominal examination, as well as an examination of any other system in response to subject-reported symptoms) will occur at all visits that do not have a full physical exam.

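### SAP 8.1's treatment-emergent definition has no end and ignores the re-entry gap, so off-drug events on the AE form count as TEAEs, while Medical History offers a second, unlisted route for the same event

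*SAP*

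**What the plan says.** **The definition.** SAP 8.1 restricts AE analysis to treatment-emergent events, where "treatment emergent is defined as any AE with onset or worsening on or after the First Study Dose in the OLE study". The anchor is a single date per subject, with no upper bound. The rule in SAP 6.3.2 for a wholly missing start date is also one-sided. It begins "If complete Adverse Event (AE) start date is missing and AE end date is on or after the date of first dose", and such an event is then counted. The last dose date appears only in the imputation of partial stop dates, for example "impute stop date as last dose date if the year is the same, otherwise December 31 of that year".

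**The gap.** SAP 4.1 states: "Subjects who already completed participation through Week 96 in PTI-125-09 will have the option to return to the study and resume participation". Re-entry is into PTI-125-09 itself. Protocol 7.2.9 adds a Week 4 visit when the gap exceeds 60 days, and no maximum gap is stated.

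**Collection at re-entry.** Protocol 7.2.8 lists both AE monitoring and "Medical History- focused on any new conditions that occurred during the gap period between study completion and study re-entry" for Re-entry Day 1, with eligibility reviewed after all assessments and before dosing. Protocol 9.1 says "Monitoring for AEs will start at dosing" and has the investigator ask about AEs since the previous assessment.

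**Output.** SAP 6.3.4 leaves medical history uncoded. SAP 7.4 says of medical and surgical history: "These will not be presented in data listings, but are available in the source documents at the sites". By contrast, SAP 6.3.2 puts all eCRF data in the safety listings, and SAP 6.4.1 promises by-subject listings of all data.

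**The concern.** The definition fits one continuous dosing course. Amendment 3 gave some subjects an on-off-on course, and SAP 8.1 was not adapted to it. The first OLE dose precedes the gap, so any gap-onset AE on the AE form satisfies the definition.

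This matters because AE displays are the only safety results left: SAP 3.1 drops the summaries of vital signs, laboratory values and ECGs. SAP 8.2 to 8.5 convert significant findings into AEs, which can include findings made at Re-entry Day 1 before the re-entry dose. SAP 6.3.2.1 then treats a missing relationship as treatment-related and a missing severity as severe. No subgroup separates re-entry subjects (SAP 6.2.2). SAP 7.1 marks them only by a disposition footnote, and SAP section 9 has no dosing listing.

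The reverse problem is that the same event entered as Medical History reaches no table and, under SAP 7.4, no listing. What is reported about the gap could then depend on which form a site used.

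**Working it through.** There is no plan figure to reproduce. The check applies the rule to a re-entry timeline and then compares the texts.

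**Inputs**
- First OLE dose on day 1; last pre-gap dose at nominal Week 96, 96 × 7 = day 672 (protocol schedule).
- Gap g days, so the re-entry dose falls on day 672 + g. The documents say only that g can exceed 60. The values below are assumptions; 61 is the shortest gap that triggers the Week 4 visit.
- Post-dose lag L = 0, 14 or 30 days (assumed; the SAP has none).

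**Formulas**
- Intervening off-drug days: g − 1.
- Treatment-emergent under SAP 8.1: all g − 1, since every one is after day 1.
- Treatment-emergent under a window that closes at lag L: min(L, g − 1).
- Excess: (g − 1) − min(L, g − 1).

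| Gap g | Off-drug days, all counted by SAP 8.1 | Excess, L = 0 | Excess, L = 14 | Excess, L = 30 |
|---|---|---|---|---|
| 30 | 29 | 29 | 15 | 0 |
| 61 | 60 | 60 | 46 | 30 |
| 90 | 89 | 89 | 75 | 59 |
| 180 | 179 | 179 | 165 | 149 |
| 365 | 364 | 364 | 350 | 334 |

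The rule counts every gap day at any gap length. It agrees with a closed window only when the gap is no longer than about the lag.

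**Study-level scale (illustration).** Assume 180 subjects with 672 days each, 180 × 672 = 120,960 days, and 10 re-entry subjects. With 61-day gaps the off-drug share of the window is 610 / (120,960 + 610) = 0.5%. With 180-day gaps it is 1,800 / (120,960 + 1,800) = 1.5%. The share grows roughly in proportion to the number who re-entered. These are shares of time, not of events.

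**Which form takes a gap event?**
- Towards Medical History: protocol 7.2.8 names gap conditions there, and 9.1 defines an AE as occurring during a study.
- Towards the AE form: AE monitoring is scheduled at the same visit (7.2.8, Appendix C), and the 9.1 prompt looks back to the last assessment, which for a re-entry subject lies before the gap.
- The sentence that monitoring starts at dosing does not decide it, because dosing first started before the gap.

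No passage says that one form excludes the other.

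**Date rules.** SAP 6.3.2 uses one first dose date and one last dose date, and does not say which last dose applies to a re-entry subject. If the pre-gap dose is used, an AE that starts later that year in the gap and has only a stop year receives a stop date before its start.

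**The case against.** The strongest reply is that the protocol leans towards Medical History for gap conditions, so few may reach the AE form. A reader might infer that SAP 8.1 makes every gap event a TEAE. It does not: entry on the AE eCRF is a precondition. What remains is an open second route, through the AE prompt and the pre-dose findings at Re-entry Day 1.

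A reader might also infer that the window stays open for everyone. For subjects who did not re-enter, scheduled AE collection ends at the End of Study / Early Termination visit, and the later duty in protocol 9.5 concerns deaths and SAEs. Collection largely bounds their window.

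Nor do the documents establish that gap Medical History disappears from all output. SAP 7.4 and section 9 point that way, but 6.3.2 and 6.4.1 say the opposite. This is a conflict to reconcile, and the data remain in site source documents. Likewise, AE start dates are collected and by-subject listings are planned, so gap AEs can in principle be placed in time. The tables cannot show this.

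Finally, an inclusive window is a defensible cautious choice for single-arm descriptive safety, and a closed one could hide late events; protocol 2.2 reports rat liver findings persisting after a 1-month recovery. That is a fair argument about the lag and for keeping every event on display. It does not justify an unlabelled mixture of on-drug and off-drug events.

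**Conclusion.** The point holds, with limited reach. As written, SAP 8.1 classes any gap-onset AE on the AE form as treatment-emergent, and the documents allow the same event to be recorded instead as uncoded Medical History.

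The effect is confined to re-entry subjects. Neither their number nor their gap lengths are given. SAP 2.1 says the program was terminated shortly after central IRB approval of Amendment 3, so few may be affected. Outputs are descriptive, with no inference or error rate at stake. The day counts assume nominal visit timing and no study drug between completion and the Re-entry Day 1 dose.

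A reader might take the 30 days in protocol 9.5 as the trial's treatment-emergent limit. The sentence opens "In the case of a death or other SAE that has occurred within 30 days after receiving study drug" and sets a reporting duty for deaths and SAEs; neither document makes it an analysis window. It is also generous as a clearance period: at the 4.5 to 6 h half-life in protocol 2.3, 30 days is 30 × 24 / 6 = 120 to 30 × 24 / 4.5 = 160 half-lives.

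**What to change.** Before database lock:

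1. In SAP 8.1, define treatment-emergent by dosing period: onset or worsening from the first OLE dose to the last pre-gap dose plus a pre-stated lag, and again from the Re-entry Day 1 dose onward. The lag is the sponsor's choice. Thirty days would match the SAE reporting period in 9.5, but the protocol does not require it.
2. Say how an onset dated Re-entry Day 1 is assigned, since that day's assessments precede the dose.
3. Flag AEs with gap onset beyond the lag as off-treatment, remove them from Tables 14.3.1.1 to 14.3.1.7, and show them in one separate listing so that no event is lost.
4. State one rule for AE versus Medical History entry of gap events. Add gap Medical History held in the eCRF to the same listing, and reconcile SAP 7.4 with 6.3.2 and 6.4.1.
5. Rewrite the missing- and partial-date rules in SAP 6.3.2 to use the first and last dose of the relevant dosing period.

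**Cost.** SAP wording, a period flag in the AE dataset, revised date programming and one listing. Subjects without a gap are unaffected. No new data are needed, unless gap history exists only in site source, as SAP 7.4 may imply despite protocol 12.1; adding those entries would require retrieval. Some events would leave the TEAE tables for the listing.
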